8.1 Lenalidomide Dose Levels (Based on Adverse Events in Table 8.31)

Table 8.11: Group A Dose Modifications[#]

Dose Level		Dose	Treatment Day	Rest Day	Route
3	Lenalidomide	25 mg	1-21	22-28	Orally
2	Lenalidomide	15 mg	1-21	22-28	Orally
1*	Lenalidomide	10 mg	1-21	22-28	Orally
-1	Lenalidomide	5 mg	1-21	22-28	Orally
-2	Lenalidomide	10 mg	Every other day, days 1-21	22-28	Orally
-3	Lenalidomide	5 mg	Every other day, days 1-21	22-28	Orally

Table 8.12: Group B Dose Modifications[#]

Dose Level		Dose	Treatment Day	Rest Day	Route
4	Lenalidomide	25 mg	1-21	22-28	Orally
3	Lenalidomide	15 mg	1-21	22-28	Orally
2	Lenalidomide	25 mg	Every other day, days 1-21	22-28	Orally
1*	Lenalidomide	15 mg	Every other day, days 1-21	22-28	Orally
-1	Lenalidomide	10 mg	Every other day, days 1-21	22-28	Orally
-2	Lenalidomide	5 mg	Every other day, days 1-21	22-28	Orally

Table 8.13: Group C Dose Modifications[#]

Dose Level		Dose	Treatment Day	Rest Day	Route
4	Lenalidomide	25 mg	1-21 [£]	22-28	Orally
3	Lenalidomide	15 mg	1-21 [£]	22-28	Orally
2	Lenalidomide	10 mg	1-21 [£]	22-28	Orally
1*†	Lenalidomide	5 mg [†]	1-21 ^{£†}	22-28	Orally
-1	Lenalidomide	5 mg	Every other day, days 1-21 [£]	22-28	Orally
-2	Lenalidomide	5 mg	Twice weekly [£]	22-28	Orally

* Starting dose level

GCSF may be used beginning in cycle 2 for neutropenia. Consistent with ASCO guidelines, the recommended starting dose for G-CSF is 5 mcg/kg/d administered subcutaneously until the occurrence of an ANC of 10,000/uL or adequate neutrophil recovery is achieved.

† The starting dose for patients in Group C accrued to dose level 1 cohort (completed September 2010) was lenalidomide 15 mg post dialysis three times weekly on Days 1-21. Starting with protocol version 5.0, if a return to dose level 1 is indicated, lenalidomide 5 mg on Days 1-21 should be used according to the package insert.

£ When a lenalidomide treatment day occurs on a dialysis day, lenalidomide must be taken after dialysis.

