1.3 Clinical Experience in Multiple Myeloma with Lenalidomide

In two phase I studies in multiple myeloma, a total of 40 patients have been treated with lenalidomide. In one study at the University of Arkansas, 15 patients who relapsed or were refractory to high dose melphalan therapy with stem cell transplant were treated for 4 weeks in an open-label safety study and were permitted to continue therapy in an extension phase of the trial.¹⁵ Patient cohorts were treated at the following daily doses: 5 mg, 10 mg, 25 mg, and 50 mg. In a similar study at the Dana Farber Cancer Institute, 25 patients with rapidly advancing refractory multiple myeloma were treated.¹⁶

Anti-myeloma activity was observed in each of these two phase I studies. Decreases in neutrophil and platelet counts were the dose-limiting toxicities associated with lenalidomide. The maximum tolerated dose (MTD) was not reached within 28 days. Due to dose modifications associated with myelosuppression observed beyond Day 28 at the 25 mg and 50 mg daily dose levels, the dose schedule most widely used in future studies has been lenalidomide 25 mg on Days 1-21, repeated every 28 days.

Pharmacokinetic analyses were performed on 15 multiple myeloma patients treated in the phase I studies.¹⁶ Absorption was found to be rapid on both Day 1 and Day 28 with time to maximum blood levels ranging from 0.7 to 2.0 hours at all dose levels (5 mg, 10 mg, 25 mg and 50 mg). Plasma lenalidomide declined in a monophasic manner with elimination half-life ranging from 2.8 to 6.1 hours on both Day 1 and 28 at all 4 doses. No plasma accumulation was observed with multiple daily dosing. Peak and overall plasma concentrations were dose proportional over the dosing range of 5 mg to 50 mg.

A multicenter, randomized, phase II trial compared 2 syncopated dose schedules of lenalidomide used alone or in combination with dexamethasone in the treatment of relapsed or refractory multiple myeloma.¹⁷ All patients were treated on Days 1-21 of a 28-day cycle. Patients treated with 15 mg BID experienced more myelosuppression and dose reductions compared with patients treated with 30 mg daily. Anti-myeloma activity was observed with each dose and schedule of single agent lenalidomide. The addition of dexamethasone to lenalidomide yielded responses in some patients who had not responded to lenalidomide alone.

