1.7 Dosing Recommendation for Lenalidomide in Patients with Renal Impairment, Hemodialysis

Chen et al.²¹ conducted a multi-center study with lenalidomide 25 mg a day as a single oral dose in five groups of subjects defined by renal function [1] normal ($\text{CrCl} >80$ mL/min); [2] mild ($\text{CrCl}: >50- <80$ mL/min); [3] moderate ($\text{CrCl}: >30- <50$ mL/min); [4] severe ($\text{CrCl} <30$ mL/min but not on dialysis); [5] End Stage Renal Disease (requiring dialysis). Thirty subjects over the age of 35 were included in the study. Subjects with normal, mild, moderate or severe renal insufficiency received a single 25 mg oral dose of lenalidomide. Subjects with end stage renal disease (ESRD) received 2 single 25 mg doses, separated by 7-10 days: one dose on a non-dialysis day and the other dose 3 hours before a 4-hour hemodialysis.²¹ Blood and urine samples were collected over 72 hours and creatinine clearance was estimated with a 24-hour urine collection (Celgene Corporation 2006). Assessments included PK and safety parameters. All subjects completed the study. Total and renal clearance of lenalidomide were strongly correlated with CrCl ($R >0.9$, $p <0.01$). As a result, AUC_∞ increased with decreasing CrCl . The mean difference in AUC_∞ between normal renal function (NRF) and mild renal insufficiency (RI) was $<20\%$. Compared with the pooled data from NRF and mild RI groups, mean AUC_∞ increased approximately 140% in moderate RI, 240% in severe RI, and 360% in ESRD (off dialysis). There was no correlation between Cmax or Tmax and

CrCl. Approximately 10% of the dose was recovered in the dialysate of subjects with ESRD. Protein binding of lenalidomide was not markedly affected by RI (~35 - 44%). The drug was well tolerated. On the basis of these data, recommendations for initial starting doses were made.

The following dose recommendations were suggested by Chen et al. for patients with MM and MDS and renal dysfunction and were based on Area Under the Curve for entire exposure to the drug (AUC 0- ∞). The lower doses of lenalidomide recommended for patients with renal dysfunction are derived from modeling to produce AUCs comparable to those produced by the administration of a 25 mg or 10 mg dose of lenalidomide, respectively, in patients with normal renal function. (Note: For previously treated multiple myeloma dosing is for 21 days of a 28-day cycle. Dosing is continued or modified based on clinical and laboratory findings.)

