8.0 Dosage Modification Based on Adverse Events for Phase I and Phase II

Treatment modifications are based on adverse events. All adverse events should be graded according to the NCI Common Terminology Criteria for Adverse Events Version 4.0 (CTCAE V4.0).

Subjects will be evaluated for AEs at each visit with the NCI CTCAE V4.0 used as a guide for the grading of severity. Refer to Tables below for specific Lenalidomide and Dexamethasone dose reduction steps. Subjects who cannot tolerate lowest dose level are to be discontinued from the treatment phase of the study. Subjects experiencing \geq grade 3 non-hematologic or grade 4 hematologic adverse events will have their study drug held per Table 8.31. Held doses are not made up. Grade 3 or 4 AEs must resolve to \leq grade 2 in severity prior to resumption of study medications. Administration of the next drug dose is to be continued with a one-level dose reduction of the relevant drug as indicated in dose reductions. Once a subject's dose has been reduced, no dose re-escalation is permitted except for a possible one-time dose escalation of lenalidomide in the event of improved renal function as described in Section 8.3.

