8.2 Lenalidomide Dose Modification Based on Hematological Toxicity (see Table 8.31 below)

8.21 Hematologic Requirements for Day 1 of Each Cycle

- ANC is $\geq 1,000/\mu\text{L}$
- Platelet count is $\geq 50,000/\mu\text{L}$

If either of these two criteria is not met, the start of the cycle should be held and CBC should be followed weekly. Once ANC and platelets have recovered to Grade 2 or less, cycle should be started at next lower dose of lenalidomide. Held doses are not made up.

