8.3 Lenalidomide Dose Modification Based On Non-Hematological Toxicity (see Table 8.31)

A one-time dose escalation in lenalidomide of one dose level is allowed at any one time point after completion of 2 cycles of treatment if one of the following conditions is met:

1. The patient was originally registered in Group C but has renal function improvement to a point that dialysis is no longer needed; or
2. The patient was originally registered in Group B but has renal function improvement to $\geq 30 \text{ CrCl (mL/min)}$.

All previously established or new toxicities observed any time, are to be managed as per Table 8.31 and Table 8.4.

If drug must be discontinued, the patient comes off treatment and goes to follow-up per Section 4.0 and event monitoring per eCRF completion guidelines. If the toxicity resolves and drug is to be restarted, the dose must be reduced by dose levels as indicated in the dose reduction table.

Please note: Held doses are not made up.

Table 8.31: Dose Modification for Lenalidomide

NCI CTC Toxicity Grade	Day 2-14 of Cycle	≥Day 15 of Cycle
Grade 3 neutropenia associated with fever (temperature $\geq 38.5^{\circ}\text{C}$) or Grade 4 neutropenia	
 Hold lenalidomide. Follow CBC weekly. If neutropenia has resolved to \leqgrade 2, restart at next lower dose level and continue the cycle until day 21. 	
 Hold lenalidomide for remainder of cycle. Restart lenalidomide next cycle (decrease dose by one dose level).
Thrombocytopenia \geq Grade 3 (platelet count $< 50,000/\text{mm}^3$)	
 Hold lenalidomide. Follow CBC weekly. If thrombocytopenia resolves to \leqgrade 2, restart lenalidomide at next lower dose level and continue the cycle through Day 21. 	
 Hold lenalidomide for remainder of cycle. Restart lenalidomide next cycle (decrease dose by one dose level).
Non-blistering rash Grade 3	
 If Grade 3, hold lenalidomide dose. Follow weekly. If the adverse event resolves to \leqgrade 1, restart lenalidomide at next lower dose level and continue the cycle through Day 21. 	
 Hold lenalidomide for remainder of cycle. Restart lenalidomide next cycle (decrease dose by one dose level).

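### In Group A's reduction table, the step from 5 mg daily to 10 mg every other day leaves total lenalidomide per cycle essentially unchanged and doubles each dose

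*Protocol*

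**What the plan says.** Section 8.1 of the protocol gives one table of lenalidomide levels per renal group. For Group A (moderate impairment), "Table 8.11: Group A Dose Modifications" runs downward as follows: 25, 15, 10 and 5 mg daily on Days 1-21 (levels 3, 2, 1 and -1), then 10 mg every other day (level -2), then 5 mg every other day (level -3).

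The text treats moving down this table as lowering the dose:

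- Section 8.0: "Administration of the next drug dose is to be continued with a one-level dose reduction of the relevant drug".
- Section 8.21, when Day 1 counts are too low: "cycle should be started at next lower dose of lenalidomide".
- Section 8.3, on restarting after toxicity: "the dose must be reduced by dose levels as indicated in the dose reduction table".
- Table 8.31, for example after neutropenia before Day 15: "restart at next lower dose level and continue the cycle until day 21".

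Neither the protocol nor the SAP explains why 10 mg every other day sits below 5 mg daily.

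**The concern.** A patient who moves from level -1 to level -2 has just had another toxicity on 5 mg daily. The protocol intends that patient to receive less drug. On total milligrams the step is close to neutral, and each dose is twice as large.

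The protocol's own pharmacology makes total dose a reasonable yardstick. Section 1.7 explains that the recommended renal doses were "derived from modeling to produce AUCs comparable to those produced by the administration of a 25 mg or 10 mg dose of lenalidomide" in patients with normal renal function, so dosing is matched on AUC. Section 1.3 reports that "Peak and overall plasma concentrations were dose proportional over the dosing range of 5 mg to 50 mg". If that holds in Group A, level -2 gives about the same exposure per cycle as level -1, with about twice the peak after each dose. A clear fall comes only at level -3, after yet another toxicity, and level -3 is the last level before discontinuation under section 8.0. Sections 1.5 and 1.6 link renal impairment to myelosuppression and dose reduction, so use of the lower levels is foreseeable.

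**Working it through.** The plan states no mg-per-cycle figure, so there is none to reproduce.

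**Inputs.** Doses and schedules are from Tables 8.11 to 8.13. Section 7.1 gives the 28-day cycle with Days 22-28 as rest.

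**Formula.** Cycle total = mg per dose × number of dosing days in Days 1-21. Daily dosing has 21 dosing days. Every-other-day dosing has 11 from a Day 1 start (1, 3, …, 21) or 10 from a Day 2 start (2, 4, …, 20). Group C's twice-weekly level is taken as 6 doses, which is an assumption.

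**The step in question (Group A, level -1 to -2).**

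- Level -1: 5 × 21 = 105 mg.
- Level -2 from Day 1: 10 × 11 = 110 mg; (110 - 105)/105 = +4.8%.
- Level -2 from Day 2: 10 × 10 = 100 mg; (100 - 105)/105 = -4.8%.
- Single dose: 5 to 10 mg, +100%.
- Dosing days: 21 to 11 (-47.6%) or 21 to 10 (-52.4%).

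**All steps, top level to bottom.**

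| Group | Every-other-day start | mg per cycle | Change at each step |
|---|---|---|---|
| A | Day 1 | 525, 315, 210, 105, 110, 55 | -40.0%, -33.3%, -50.0%, **+4.8%**, -50.0% |
| A | Day 2 | 525, 315, 210, 105, 100, 50 | -40.0%, -33.3%, -50.0%, **-4.8%**, -50.0% |
| B | Day 1 | 525, 315, 275, 165, 110, 55 | -40.0%, -12.7%, -40.0%, -33.3%, -50.0% |
| B | Day 2 | 525, 315, 250, 150, 100, 50 | -40.0%, -20.6%, -40.0%, -33.3%, -50.0% |
| C | Day 1 | 525, 315, 210, 105, 55, 30 | -40.0%, -33.3%, -50.0%, -47.6%, -45.5% |
| C | Day 2 | 525, 315, 210, 105, 50, 30 | -40.0%, -33.3%, -50.0%, -52.4%, -40.0% |

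There are five steps per group, 15 in all. Fourteen lower the total by at least 12.7%; the smallest of these is Group B level 3 to 2. Group C also steps down from 5 mg daily, but goes directly to 5 mg every other day.

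**Exposure.** With AUC and peak proportional to dose, cycle AUC at level -2 relative to level -1 is 100/105 = 95.2% (Day 2 start) to 110/105 = 104.8% (Day 1 start). Peak per dose is 10/5 = 2.0 times.

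**Mid-cycle restart under Table 8.31.** With k dosing days left, counting the restart day as the first dose, level -1 would give 5k mg and level -2 gives 10 × ceil(k/2) mg. The difference is 0 mg when k is even and 5 mg more at level -2 when k is odd. For k = 7: 35 mg against 40 mg.

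**Every-other-day options.** Section 15.15 supplies 5 mg and 25 mg capsules, and section 7.11 requires them to be swallowed whole. The cycle totals are 50-55 mg for 5 mg, 100-110 mg for 10 mg and 150-165 mg for 15 mg. Against 105 mg, only 5 mg is clearly lower.

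**The case against.** The best counter-argument is that the row is a deliberate change of schedule. The protocol never defines a dose level by its cycle total, so no stated figure is wrong. Group B also moves from daily to a larger every-other-day dose (15 to 25 mg), so a bigger single dose lower in the table is not in itself a slip. Dosing days do roughly halve, and with the short half-life in section 1.3 (2.8 to 6.1 hours) a 48-hour interval could allow recovery. The one same-total comparison in the documents points that way: "Patients treated with 15 mg BID experienced more myelosuppression and dose reductions compared with patients treated with 30 mg daily". No text ties peak concentration to toxicity. The proportionality result comes from 15 phase I patients whose renal function is not given.

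Part of this stands. Fewer dosing days might improve tolerability, and the documents cannot show that level -2 is as toxic as level -1. It does not rescue the row as written. The Group B step lowers the total by 12.7% or 20.6%; this one does not. The comparison of 15 mg twice daily with 30 mg once daily concerns splitting within a day, so it does not settle whether doubled doses on alternate days are safer. No schedule rationale is stated, while sections 8.0, 8.21 and 8.3 all describe the step as a lower dose.

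It is also fair that existing rules limit harm. Grade 3-4 events must recover to grade 2 or less before restart, held doses are not made up, for most toxicities from Day 15 lenalidomide is held for the rest of the cycle, and some toxicities require discontinuation.

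**Conclusion.** The concern holds. Group A level -2 is not a meaningful reduction from level -1: the cycle total changes by +4.8% or -4.8% depending on the first dosing day, and each dose doubles. It is the only one of the 15 steps that behaves this way.

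The milligram totals rest only on the table and the dosing calendar. The statement about exposure also assumes that dose proportionality extends to moderate renal impairment. Whether toxicity would be the same at the two levels is not established.

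The reach is small. It concerns Group A patients already on 5 mg daily who have a further toxicity requiring reduction: the second reduction from a 10 mg start, the third from 15 mg (the level open in November 2010) and the fourth from 25 mg. The Phase I escalation levels, the MTD rule and the Phase II primary analysis are not affected. It is a patient-safety correction worth making because the rule does not do what the protocol says it does.

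**What to change.** Delete the 10 mg every-other-day row from Table 8.11, so that 5 mg daily (105 mg) steps to 5 mg every other day (50-55 mg), as in Table 8.13. The clinical team should confirm the level.

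The cost is one table correction in the next amendment and a notice to sites. Group A would then have two levels below its starting dose instead of three, the same number as Groups B and C, so some patients may reach discontinuation one step sooner. If a third level is wanted, add 5 mg twice weekly (6 × 5 = 30 mg) as the lowest. Table 8.13 already uses that regimen, though for dialysis patients, so its use in Group A also needs clinical agreement.

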8.2 Lenalidomide Dose Modification Based on Hematological Toxicity (see Table 8.31 below)

8.21 Hematologic Requirements for Day 1 of Each Cycle

- ANC is $\geq 1,000/\mu\text{L}$
- Platelet count is $\geq 50,000/\mu\text{L}$

If either of these two criteria is not met, the start of the cycle should be held and CBC should be followed weekly. Once ANC and platelets have recovered to Grade 2 or less, cycle should be started at next lower dose of lenalidomide. Held doses are not made up.

8.3 Lenalidomide Dose Modification Based On Non-Hematological Toxicity (see Table 8.31)

A one-time dose escalation in lenalidomide of one dose level is allowed at any one time point after completion of 2 cycles of treatment if one of the following conditions is met:

1. The patient was originally registered in Group C but has renal function improvement to a point that dialysis is no longer needed; or
2. The patient was originally registered in Group B but has renal function improvement to $\geq 30 \text{ CrCl (mL/min)}$.

All previously established or new toxicities observed any time, are to be managed as per Table 8.31 and Table 8.4.

If drug must be discontinued, the patient comes off treatment and goes to follow-up per Section 4.0 and event monitoring per eCRF completion guidelines. If the toxicity resolves and drug is to be restarted, the dose must be reduced by dose levels as indicated in the dose reduction table.

Please note: Held doses are not made up.

Table 8.31: Dose Modification for Lenalidomide

NCI CTC Toxicity Grade	Day 2-14 of Cycle	≥Day 15 of Cycle
Grade 3 neutropenia associated with fever (temperature $\geq 38.5^{\circ}\text{C}$) or Grade 4 neutropenia	
 Hold lenalidomide. Follow CBC weekly. If neutropenia has resolved to \leqgrade 2, restart at next lower dose level and continue the cycle until day 21. 	
 Hold lenalidomide for remainder of cycle. Restart lenalidomide next cycle (decrease dose by one dose level).
Thrombocytopenia \geq Grade 3 (platelet count $< 50,000/\text{mm}^3$)	
 Hold lenalidomide. Follow CBC weekly. If thrombocytopenia resolves to \leqgrade 2, restart lenalidomide at next lower dose level and continue the cycle through Day 21. 	
 Hold lenalidomide for remainder of cycle. Restart lenalidomide next cycle (decrease dose by one dose level).
Non-blistering rash Grade 3	
 If Grade 3, hold lenalidomide dose. Follow weekly. If the adverse event resolves to \leqgrade 1, restart lenalidomide at next lower dose level and continue the cycle through Day 21. 	
 Hold lenalidomide for remainder of cycle. Restart lenalidomide next cycle (decrease dose by one dose level).
Grade 4	
 Discontinue lenalidomide study drug and go to follow-up and event monitoring. 	
 Discontinue lenalidomide study drug and go to follow-up and event monitoring.
Desquamating (blistering) rash- any Grade	
 Discontinue lenalidomide study drug and go to follow-up and event monitoring. 	
 Discontinue lenalidomide study drug and go to follow-up and event monitoring.
Erythema multiforme \geq Grade 3	
 Discontinue lenalidomide study drug and go to follow-up and event monitoring. 	
 Discontinue lenalidomide study drug and go to follow-up and event monitoring.
Sinus bradycardia/other cardiac arrhythmia Grade 2 \geq Grade 3	
 Hold lenalidomide dose. Follow at least weekly. If the adverse event resolves to \leqgrade 1, restart lenalidomide at next lower dose level and continue the cycle through Day 21. 	
 Hold lenalidomide for remainder of cycle. Restart lenalidomide next cycle (decrease dose by one dose level).
	
 Discontinue lenalidomide study drug and go to follow-up and event monitoring. 	
 Discontinue lenalidomide study drug and go to follow-up and event monitoring.

Allergic reaction or hypersensitivity Grade 2-3	
 Hold lenalidomide dose. Follow at least weekly. If the adverse event resolves to \leqgrade 1, restart lenalidomide at next lower dose level and continue the cycle through Day 21. 	
 Hold lenalidomide for remainder of cycle. Restart lenalidomide next cycle (decrease dose by one dose level).
Grade 4	
 Discontinue lenalidomide study drug and go to follow-up and event monitoring. 	
 Discontinue lenalidomide study drug and go to follow-up and event monitoring.
Venous thrombosis/embolism \geq Grade 3	
 Hold lenalidomide and start therapeutic anticoagulation; restart lenalidomide at investigator's discretion (maintain dose level). 	
 Hold lenalidomide for remainder of cycle. See Anticoagulation Consideration (see Section 9.4). Restart lenalidomide next cycle (decrease dose by one dose level).
Hyperthyroidism or hypothyroidism \geq Grade 3	
 Hold lenalidomide for remainder of cycle, evaluate etiology, and initiate appropriate therapy. Restart lenalidomide next cycle (decrease dose by one dose level) 	
 Hold lenalidomide for remainder of cycle, evaluate etiology, and initiate appropriate therapy. Restart lenalidomide next cycle (decrease dose by one dose level).
Other non-hematologic adverse events assessed as lenalidomide related \geq Grade 3	
 Hold lenalidomide dose. Follow at least weekly. If the adverse event resolves to \leqgrade 2, restart lenalidomide and continue through the scheduled Day 21 of current cycle. Otherwise, hold for remainder of cycle. Held doses are not made up. For toxicity attributed to lenalidomide, reduce by one dose level when restarting lenalidomide. 	
 Hold lenalidomide for remainder of cycle. Restart lenalidomide next cycle (decrease dose by one dose level).

